9.2.3 Documentation of Screening Failures

During screening, patients may prove to be ineligible for participation in the study. The following documents and data should be collected in the eCRF for screening failures:

- Signed ICF
- Demography
- In/exclusion criteria which were not fulfilled by the patient
- Information on AEs (recording or confirmation that none occurred)

No other data will be entered in the eCRF for Screen Failure patients.

9.2.4 Pregnancy and Risks Counselling

In addition, pregnancy and risk counselling will be conducted during the screening period.

9.2.5 Subject Numbering

Each patient is identified in the study by a 7 digit Subject Number, which is assigned when the patient is enrolled for screening and is retained as the primary identifier for the patient throughout study participation. The Subject Number (Subject No.) consists of the country number (two digits), the Center Number (three digits) as assigned by Morphosys to the investigative site with a sequential patient number (two digits) suffixed to it, so that each patient is identified. Upon signing the informed consent form, the patient is assigned to the next sequential Subject Number available to the Investigator.

Once assigned, the Subject No. must not be reused for any other patient.

9.2.6 Re-screening

Patients can be re-screened at the discretion of the Investigator under certain circumstances. Re-screening is restricted to one attempt per patient and can only be performed if any of the following criteria is met:

1. The patient has already consented and met all of the inclusion and none of the exclusion criteria and his or her enrolment was delayed due to an unexpected change in the patient's personal situation (e.g., family issues).
2. The patient previously failed to be eligible due to any event (e.g., planned surgery, laboratory test result) or any technical/logistic reason (e.g. screening period elapsed due to unexpected leave or absence of patient) that has been resolved.
3. The patient previously failed screening but has become eligible for the study based on a change in the inclusion and exclusion criteria as the result of a protocol amendment.

A patient should only be re-screened if there is a clear indication that the patient may be eligible according to the currently valid study protocol.

In cases where previous screening activities were discontinued and enrolment did not occur, the following procedures should be implemented:

1. The patient must sign and date a new informed consent form (ICF) as part of the re-screening procedure.
2. A new Subject ID will be assigned to the patient.
3. The patient will be documented as re-screened in the source documents.
4. A recording of medical histories, physical examinations, prior treatments for CLL/SLL, AEs, and concurrent medications will be transcribed from the previously used to the new eCRF if the conditions and medications still apply to the current status of the re-screened patient as documented in the source documents. All screening procedures must be completed again.

A re-screened patient can be enrolled, if all of the current inclusion criteria and none of the exclusion criteria are met.

9.2.7 Treatment Period

The treatment period consists of a total of 24 cycles, each cycle lasting 28 days. For the first 3 months (3 cycles) of the study each 28-day cycle will consist of a MOR00208 infusion on Day 1, Day 8, Day 15 and Day 22 of the cycle. In addition, a loading dose will be administered on Day 4 of Cycle 1. Thereafter, MOR00208 will be administered on a biweekly basis (every 14 days) with infusions on Day 1 and Day 15 from Cycle 4 to Cycle 6. MOR00208 will be given on a monthly basis on Day 1 from Cycle 7 to Cycle 24.

One to four visits are foreseen for each treatment cycle. Day 1 is the main visit of each cycle, where the largest number of examinations and assessments will be performed (for detail, see [Table 10](#)). Idelalisib or venetoclax tablets will be handed to the patients on Day 1 of each cycle.

Patients who continue to derive benefit from therapy with MOR00208 can stay on MOR00208-treatment even beyond Cycle 24. In this case, the patient should be followed up at further visits (C25D1, C26D1, etc.) as specified for Cycle 7 to Cycle 24 (see the Schedule of Assessments, [Table 10](#)). Examinations which are not performed on every cycle, e.g., radiological and PK examinations, should also be followed up according to the specifications made in [Table 10](#).

Patients who achieved a confirmed CR or PR with bone marrow MRD negativity are allowed to stop idelalisib or venetoclax treatment and proceed with monthly MOR00208 treatment per discussion between the Investigator and sponsor's medical monitor.

9.2.8 Unscheduled Visit

The Investigator may at his/her discretion arrange for a patient to have an unscheduled assessment, especially in the case of AEs that require follow-up or an AE considered by the Investigator to be possibly related to the use of study drug. The unscheduled visit page in the CRF must be completed.

Ramp-up phase of venetoclax will be performed at regular scheduled visits. In cases when dose modification of venetoclax needs to be performed at an unscheduled visit (e.g., due to dosing interruption or reduction of venetoclax which leads to changed treatment schedule of venetoclax), the following evaluations and safety measures should be performed at respective unscheduled visit to reinstate the weekly dosing of venetoclax:

- Risk reassessment and prophylaxis for TLS (see Sections [8.5](#), [8.10.1](#) and [9.3.2.6](#))
 - Evaluation and monitoring of blood chemistry locally (e.g., potassium, uric acid, phosphorus, calcium, and creatinine)
 - Assessment of tumor burden (ALC, physical examination), and comorbidities or symptoms suggestive of TLS
- Hospitalization as prescribed
- Central laboratory of hematology and serum chemistry. Other laboratory parameters (e.g., coagulation parameters, urinalysis) may be determined only if clinically indicated
- Vital signs
- 12-lead resting ECG, only if clinically indicated
- Recording of (S)AEs

9.2.9 End of Treatment Visit

Patients will continue on study treatment until documented disease progression, intolerable toxicity, withdrawal of consent to continue study treatment, death, physician decision or early termination of the study. At that time, an End of Treatment (EOT) visit will be performed.

Assessments are to be completed preferably within ≤ 30 days of last study medication intake. The EOT visit will involve:

- Documentation of concomitant medications
- Blood sampling B-/T-/NK-cell count, CD19 expression assessment (see Section [9.3.6](#)), for anti-MOR00208 antibodies (Section [9.3.5](#)), MOR00208 PK sample (see Section [9.3.4](#)) and a MRD assessment (only in case of CR or PR; see Section [9.3.3.6](#))

- Disease response assessment of CLL and SLL (CT or MRI scans of neck, chest, abdomen, pelvis)
- Bone marrow aspiration and biopsy (**required** for confirmation of CR)
- B-symptoms (see Section 9.3.3.5)
- Serum pregnancy test for FCBP (see Section 9.3.2.1)
- ECOG performance status (see Section 0)
- Blood sampling for hematology, serum chemistry and coagulation (central laboratory) (see Section 9.3.2.5)
- Urinalysis (see Table 11)
- Complete physical examination (see Section 9.3.2.3)
- Vital signs and weight (see Section 9.3.2.2)
- 12-lead resting ECG (see Section 9.3.2.4)
- Recording of (S)AEs (see Sections 10.2 and 10.5)

Assessments can take place within 7 days of the actual EOT visit.

9.2.10 Follow-up Period

9.2.10.1 30-Day Safety Follow-up Visit

Regardless of the reason for study drug discontinuation, patients will have a safety follow-up visit scheduled 30 days after the last dose of the study treatment to follow up for AEs and SAEs that may have occurred after discontinuation from the study treatment.

9.2.10.2 Follow-up for Drug Discontinuation/Patient Withdrawal from Study

If a patient discontinues study treatment and is withdrawn from the study for any reason, the study site should immediately notify the medical monitor. The date and the reason for study discontinuation must be recorded on the eCRF. Patients who discontinue prematurely are to attend an EOT visit, if possible, and complete all assessments.

In the event that a patient discontinues prematurely from the study due to a TEAE or serious TEAE, the TEAE or serious TEAE will be followed until it resolves (returns to normal or baseline values) or stabilizes, or until it is judged by the Investigator to be no longer clinically significant.

Once a patient is withdrawn from the study, the patient may not re-enter the study.

9.3 Study Assessments

9.3.1 Demographic Characteristics and Other Baseline Assessments

9.3.1.1 Weight/Height

Body weight (reported in kilogram, kg) and body height should be measured with clothes on but without shoes. Height will be measured at C1D1 only, and weight should be measured at each visit. The values should be entered into the eCRF indicating the actual day of measurement.

For inpatients, body weight can be measured up to 24 hours before study drug administration on Day 1 of each cycle. This baseline weight will be used to calculate the study drug dose during the given cycle provided the weight does not deviate more than $\pm 10\%$ from baseline during the course of this cycle. In case body weight changes more than $\pm 10\%$ from baseline, the current weight will be used to calculate the next and subsequent doses of study drug.

For outpatients, the patient weight must be measured on Day 1 of each cycle. This baseline weight will be used to calculate the study drug dose during the given cycle, provided the patient confirms that their body weight has not changed more than $\pm 10\%$ from baseline. In case body weight changes more than $\pm 10\%$ from baseline, the current weight will be used to calculate the next and subsequent doses of study drug.

For both in- and outpatients, weight measurement will need to be performed at each visit and the values will need to be entered into the eCRF indicating the actual day of measurement. For outpatients, weight measurement may take place pre- or post dose.

9.3.1.2 Demography

Demographic baseline characteristics include age (including date of birth), sex and race.

9.3.1.3 Medical History/Current Medical Conditions

Medical history deserves particular attention because it is paramount for eligibility. Relevant medical history and current medical conditions will be recorded at the time of signing of the ICF. The medical history of CLL/SLL should be documented in detail, including baseline symptoms as well as a detailed history of prior cancer therapies for CLL/SLL, with start and stop dates, disease progression during or after therapy, as well as discontinuations due to intolerability or any other clinically significant illness. Any previous therapy (e.g., chemotherapy, immunotherapy, or radiation therapy) for CLL/SLL should be recorded in the eCRF.

Findings supporting the diagnosis of the latest progression of CLL/SLL should be recorded in the patient's source documents. Such findings may consist of laboratory examinations, imaging results or clinical symptoms related to CLL/SLL.

9.3.1.4 Disease Staging

Assessments at baseline should also include Binet and modified Rai staging. For details please refer to [Appendix A](#).

9.3.1.5 FcγRII/III Gene Mucosal Cheek Swab

Before study drug administration, mucosal cheek swabs should be done for FcγR genotyping. The assessment is optional (also see [Table 13](#)).

9.3.2 Assessment of Safety

9.3.2.1 Pregnancy Testing

For FCBP, two pregnancy tests must be performed; the first, a serum pregnancy test (β -HCG) at screening within 7 days prior to the start of study drug, and the second, a local urine pregnancy test within 24 hours prior to the start of study drug. The results of both tests must be negative in order to receive C1D1 dosing. A β -HCG serum pregnancy test should also be performed at the EOT visit. At all other timepoints indicated in the Schedule of Assessments (Table 10), a urine pregnancy test for FCBP will be performed locally and the result must be negative for dosing.

9.3.2.2 Vital Signs

Vital signs will be measured at the timepoints described in the Schedule of Assessments (Table 10). These assessments include body temperature, systolic and diastolic blood pressure readings (mmHg), heart rate (beats per minute [bpm]), and respiratory rate (breaths per minute [brpm]).

Vital signs will be measured immediately prior to infusion, 15 ± 5 minutes, 30 ± 10 minutes, and then every 60 ± 15 minutes during infusion, and at end of infusion (± 20 min). The actual time of vital sign measurements should be accurately documented. If the infusion is interrupted and/or subsequently restarted, vital signs should be assessed every 60 ± 15 minutes after the first hour.

During the safety run-in phase the following measures need to be performed on Cycle 1 Day 1 and Cycle 1 Day 4:

- Patients No. 1-3 (safety run-in phase): vital signs should be measured 1 hour after end of infusion (± 20 min) and 2 hours after end of infusion (± 20 min).
- Patients No. 4- approximately 12 (safety run-in phase): vital signs should be measured 1 hour after end of infusion (± 20 min).

The frequency or the length of the monitoring period may be adapted if clinically indicated, e.g., if in the opinion of the Investigator the vital sign results, at the time of event onset, are clinically significant. In such a case the patient's vital sign measurements should continue to be recorded until they have returned to normal or pre-infusion levels and an AE recorded. If possible, before vital signs are measured, the patient should be resting for at least 5 minutes. The same position should be used each time vital signs are measured for a given patient, and blood pressure should be measured from the arm contralateral to the site of study drug administration. Body temperature should be measured according to normal institutional practice.

9.3.2.3 Physical Examination

A complete physical examination (PE) will be performed by the Investigator or a qualified designee during the screening and at the EOT visit.

Complete PE must be performed according to the best standards of local medical practice, but should include at least palpable tumor assessment, general appearance, skin, head, eyes, ears, nose, throat including Waldeyer lymphatic structures, lungs, breasts and axillae, cardiovascular system, back and spine, abdomen, extremities, infusion site, lymph nodes, and neurological examination.

Limited PEs may be focused on tumor response assessment (lymph nodes, liver, spleen, etc.) and AEs (e.g., attention on respiratory signs and symptoms) at the Investigator's discretion. Such limited PEs will be performed as indicated in the Schedule of Assessments (Table 10). Limited

PE will be performed on Day 1 and 15 of Cycle 1 to 6, on Day 1 of all further visits, and at EOT. Symptom-driven full PEs may be performed as clinically indicated at any study visit.

9.3.2.4 Electrocardiogram

Standard 12-lead resting ECGs should be obtained at the various timepoints described in the Schedule of Assessments (Table 10). ECGs should be recorded after the patient has rested in a supine position for at least 5 minutes. Heart rate, PR, QRS, RR and QT intervals should be determined. All ECGs should be performed and interpreted locally. The Investigator should evaluate the clinical significance of each value outside the reference ranges according to the nature and degree of the observed abnormality. Any new abnormal values considered to be clinically significant should be reported as AEs.

If clinically significant abnormalities are observed or artefacts are present that result in an inability to adequately interpret the results, the ECG should be repeated. An average of all intervals measured in all ECG tracings recorded at a given timepoint may be taken if necessary.

9.3.2.5 Laboratory Assessments

Clinical laboratory tests should be performed according to Table 10 and Table 11. During the course of the study, local (“emergency”) and central laboratories will be used.

Central laboratory results are required for determining patient eligibility for study enrolment and will be used in the statistical analysis of the study results. During the course of the study, all scheduled central laboratory results should be reviewed as soon as possible after Day 1 of each cycle.

It is permitted to repeat on a single occasion the central laboratory assessment of serum chemistry and hematology parameters during screening due to the variability of the parameters and their dependence on a multitude of factors (see Section 9.2.2).

Table 11: Safety Laboratory Evaluations

Evaluation	Analysis
“Emergency laboratory” (EDTA blood and serum sample)	AST, ALT, bilirubin (total, direct and indirect), direct Coombs test, hemoglobin, platelets, potassium, serum creatinine, sodium, WBCs, including WBC differential (including ANC) ¹ Cohort B only: Additional values to be analyzed: calcium, creatinine, inorganic phosphorus (phosphate), potassium and uric acid
Hematology (EDTA blood)	Direct Coombs test, erythrocyte count (RBC count), hematocrit, hemoglobin, mean corpuscular hemoglobin, mean corpuscular hemoglobin concentration, mean corpuscular volume, platelet count, reticulocytes, WBC with differential count (absolute counts and % of leukocytes: basophils, eosinophils, lymphocytes, monocytes, neutrophils) At screening: should include a peripheral blood smear.
Serum chemistry (serum sample)	ALT, total albumin, ALP, amylase, AST, β_2 -microglobulin, bicarbonate, bilirubin (total, direct and indirect), blood urea nitrogen, calcium (total), chloride, cholesterol, creatinine, creatinine kinase, GGT, glucose, LDH, lipase, magnesium, phosphate, potassium, protein (total), serum CrCl calculated using a standard Cockcroft-Gault formula, sodium, triglycerides, uric acid
Coagulation parameters (sodium citrate blood)	Activated partial thromboplastin time, prothrombin time, international normalized ratio
Viral parameters (serum or plasma sample)	Hepatitis B: HBsAg, anti-HBc and HBsAb. HBV DNA if anti-HBc positive, optional Hepatitis C: HCV antibody (HCV RNA quantification if anti-HCV positive) CMV: CMV antibody and CMV copy number per mL (PCR based) HIV-1/-2 Ag and Ab Screening (HIV-1/-2 Ab differentiation if HIV positive)
Pregnancy test (serum sample)	β -HCG serum, females of childbearing potential only
Pregnancy test (urine)	β -HCG urine, females of childbearing potential only
Urinalysis	Clarity (clear, slightly cloudy, cloudy, turbid), bilirubin, color, glucose, hemoglobin, ketones, leukocyte esterase, nitrite, pH, protein, specific gravity, urobilinogen. Microscopy will only be performed if clinically indicated.

Abbreviations: ALP= alkaline phosphatase; ALT=alanine transaminase; anti-HBc=hepatitis B core antibody; ANC=absolute neutrophil count; AST=aspartate amino-transferase; β -HCG=beta-human chorionic gonadotropin; CMV=Cytomegalovirus; CrCl=creatinine clearance; DNA=deoxyribonucleic acid; EDTA=ethylenediaminetetraacetic acid; GGT=gamma-glutamyltransferase; HBsAb=hepatitis B surface antibody; HBsAg=hepatitis B surface antigen; HBV=hepatitis B virus; HIV=human immunodeficiency virus; LDH=lactate dehydrogenase; PCR=polymerase chain reaction; RNA= ribonucleic acid; RBC=red blood cell; WBC=white blood cells.

¹WBC differential can be automated or manual as per institutional standards. Reticulocytes may be determined only if clinically indicated.

Local (“emergency”) laboratory results will be used for treatment or clinically related decisions, or for the immediate safety needs of a study patient. “Emergency laboratory” (local) results should be reviewed as soon as possible after their receipt and before dosing so that the administration of the investigational medicinal product may be adjusted or interrupted if necessary. Emergency laboratory assessments may be performed up to 24 hours before administration of study drugs.

Detailed instructions and amounts of biological samples needed for the respective laboratory measurements will be summarized in the Laboratory Manual. All samples will be collected as non-fasting samples.

[Table 11](#) summarizes laboratory assessments for a safe study conduct and for the evaluation of safety.

Safety and Hematology Laboratory Testing

The laboratory results of the centrally assessed clinical and safety relevant parameters will automatically be entered into the eCRF. The signed and interpreted laboratory results (both local and central) are to be kept in the patient’s source documentation. The laboratory results should be reviewed, dated and signed in a timely manner by the Investigators. Any clinically significant discrepancies between local and central laboratory results will be evaluated by the Investigator and medical monitor on a case-by-case basis. All blood samples should be processed and handled according to standard laboratory procedures. The time of blood collection should be documented in the eCRF.

Any abnormal laboratory findings (identified either through local or central laboratory analysis) that constitute an AE should be reported as such and should be followed up until the outcome is known. Also, additional diagnostic tests may be indicated to determine a more precise diagnosis of the patient’s condition (e.g., ordering a white blood cell [WBC] differential count to help characterise a high or low WBC count, or ordering a determination of red blood cell [RBC] indices to help characterise a low hematocrit).

Virus Serology

Patients will be examined according to the Schedule of Assessments ([Table 10](#)) for viral hepatitis B / C, HIV and Cytomegalovirus (CMV) serology.

Hepatitis B and C

Hepatitis B biomarkers include hepatitis B surface antigen (HBsAg), total hepatitis B core antibody (anti-HBc) and hepatitis B surface antibody (HBsAb). For patients who are positive for anti-HBc, hepatitis B viral DNA (HBV DNA) should be measured.

Seropositive for or active viral infection with HBV:

- a) HBsAg positive
- b) HBsAg negative, HBsAb positive and/or anti-HBc positive and detectable viral DNA.
Note: patients who are HBsAg negative and viral DNA negative are eligible
- c) Patients who had HBV but have received an antiviral treatment and show no detectable viral DNA for 6 months prior to the time of signing of the ICF are eligible

- d) Patients who exhibit the classical vaccination profile of HBsAb positive, anti-HBc negative, and HBsAg negative are eligible.

If HBV DNA becomes detectable during treatment, patients should be prophylactically treated and followed-up for potential hepatitis B reactivation as per local medical practice or institutional guidelines for CD20 antibodies such as RTX. If the HBV DNA assay is positive, then patients can only stay in the study if they are assessed by a physician experienced in the treatment of hepatitis B and pre-emptive treatment is initiated, if deemed appropriate, and/or according to local practice/guidelines.

Hepatitis C serology is to be done at screening only. Hepatitis C biomarkers include hepatitis C virus antibody (anti-HCV). For patients who are positive for anti-HCV, HCV RNA should be measured.

A positive hepatitis C test is defined as a positive test for anti-HCV and a positive test for HCV RNA.

HIV

Currently, there are no safety data on the use of CD19 antibodies in HIV positive patients available. Patients with known HIV infections will therefore be excluded from the clinical trial. In order to ensure that this patient population (which may also include patients with positive but unknown HIV status) will be adequately identified all patients must undergo HIV testing during screening. HIV testing during screening will be done using standard antibody tests.

Cytomegalovirus

A central CMV laboratory test (serology and PCR) will be performed for all patients at screening. Patient with negative serology should be monitored locally in accordance with institutional guidelines. Patients with positive serology or with other evidence of a history of CMV infection should be carefully monitored with a PCR based methodology:

- monthly, if the initial PCR result was negative without associated clinical signs of CMV infection
- weekly, if significant CMV viremia is detected.

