	
 a) CNS primary or secondary malignancy in present or past medical history (unless patient has been free of the disease for ≥ 5 years prior to screening)¹ b) CNS, meningeal or epidural malignancies (e.g., brain metastases, known leukemic meningeosis)¹ ¹ Note: Screening for cerebrospinal fluid (CSF)/CNS involvement is not required but may be performed at the discretion of the Investigator. c) CNS lesions/cerebrovascular event(s) with clinically significant sequelae d) history or evidence of clinically significant cerebrovascular CNS that would in the Investigator's opinion preclude participation in the study or compromise the patient's ability to give informed consent. 
11. Patients with:
 
 a) chronic diarrhoea and malabsorption syndrome b) any evidence of ongoing systemic viral, bacterial, or fungal infection (including Pneumocystis jirovecii pneumonia and Cytomegalovirus infection) c) history of serious allergic reactions including anaphylaxis and toxic epidermal necrolysis d) Cohort A only: ongoing inflammatory bowel disease as ulcerative colitis or Crohn's disease e) Cohort A only: severe chronic obstructive pulmonary disease (COPD), pulmonary emphysema or drug-induced pneumonitis diagnosed in previous medical history 
12. Patients with known seropositivity for or history of active viral infection with human immunodeficiency virus (HIV) (Additional information: no safety data on the use of CD19 antibodies in HIV positive patients are currently available)
 
13. Patients with known positive hepatitis B and/or C serology (as defined in the protocol).

Dose, Route of Administration, Treatment Regimen
	
Patients will be treated with MOR00208 and idelalisib or venetoclax for up to 24 cycles at maximum or until progression of disease, withdrawal of consent, unacceptable toxicity, death or patient is lost to follow-up, whichever occurs first.
 
MOR00208 dose: 12 mg/kg For the first 3 months of the study, each 28-day cycle will consist of a MOR00208 intravenous infusion of the dose of 12 mg/kg on Day 1, Day 8, Day 15 and Day 22 of the cycle. Additionally, a loading dose will be administered on Day 4 of Cycle 1. Thereafter, MOR00208 will be administered on a biweekly basis (every 14 days) with infusions on Days 1 and 15 of each cycle from Cycle 4 to 6, and on a monthly basis on Day 1 of each cycle from Cycle 7.
 
Idelalisib dose:

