7.2 Patient Selection Criteria

All patients must sign informed consent and meet the following selection criteria at screening and baseline to participate in the study.

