 - e) **Cohort A only:** severe chronic obstructive pulmonary disease (COPD), or pulmonary emphysema or drug-induced pneumonitis diagnosed in previous medical history

12. Patients with known seropositivity for or history of active viral infection with human immunodeficiency virus (HIV). (Additional information: no safety data on the use of CD19 antibodies in HIV positive patients are currently available)
13. Patients with known positive hepatitis B and/or C serology
 - a) hepatitis B virus (HBV): patients with positive serology for HBV, defined as positivity for hepatitis B surface antigen (HBsAg) or total hepatitis B core antibody (anti-HBc). (Note: Patients positive for anti-HBc may be included if HBV DNA is not detectable, but have to be monitored in 2-month intervals via HBV DNA testing)
 - b) hepatitis C virus (HCV): patients with positive HCV serology (defined as positive for HCV antibody [anti-HCV]) unless confirmed negative for HCV-ribonucleic acid (RNA)

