9.2.2 Screening Period

The Screening Period begins on the date when the ICF is signed; it will last for up to 28 days and is followed by Cycle 1 Day 1 (C1D1). In exceptional cases, the screening period may be extended at the discretion of the investigator for a total of up to 42 days due to any technical/logistic reasons (e.g., extended imaging equipment breakdown and/or servicing, delays in the delivery of central laboratory results). The reason for such extension along with an evaluation by the investigator ensuring that such extension does not pose any health risk for the patient should be documented in the patient's source data.

The assessments to be performed at screening may be grouped as follows:

- Assessment of in/exclusion criteria (see Section 7.2.1 and 7.2.2)
- Pregnancy and risks counselling; pregnancy test for FCBP. Two pregnancy tests must be performed: the first, a serum pregnancy test at screening within 7 days prior to the start of study drug and the second, a local urine pregnancy test within 24 hours prior to the start of study drug. The results of both tests must be negative in order to receive C1D1 dosing (see Section 9.3.2.1).
- Documentation of demography, medical history, previous/concomitant medications, weight/height (see Section 9.3.1)
- Disease assessment of CLL and SLL (CT or MRI scan of neck, chest, abdomen, pelvis) within 14 days before C1D1 (see Sections 9.3.3.1 and 9.3.3.3)
- ECOG performance status (see Section 9.3.8)

- Disease staging (see [Appendix A](#))
- B-symptoms (see Section [9.3.3.5](#))
- Complete physical examination (see Section [9.3.2.3](#))
- Vital signs (see Section [9.3.2.2](#))
- 12-lead resting ECG (see Section [9.3.2.4](#))
- Blood sampling for hematology, serum chemistry and coagulation (central laboratory) (see Section [9.3.2.5](#))
- Viral testing: hepatitis B and C, CMV, HIV (see [Virus_Serology](#))
- Urinalysis (see [Table 11](#))
- Recording of (S)AEs (see Section [10.5](#))

The assessments performed during screening will be used for generating the baseline data.

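### Hepatitis B rules disagree: exclusion 13a requires HBV DNA testing that Table 11 calls optional and Table 10 does not name, and one eligibility item omits HBsAg status

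*Protocol*

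**What the plan says.** **Entry rule.** Protocol 7.2 makes the selection criteria compulsory: "All patients must sign informed consent and meet the following selection criteria at screening and baseline". Exclusion 13a in 7.2.2 removes "patients with positive serology for HBV, defined as positivity for hepatitis B surface antigen (HBsAg) or total hepatitis B core antibody (anti-HBc"). Its Note gives one exception: anti-HBc-positive patients "may be included if HBV DNA is not detectable, but have to be monitored in 2-month intervals via HBV DNA testing".

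**Section 9.3.2.5, Hepatitis B and C.** The text asks for the DNA test: "For patients who are positive for anti-HBc, hepatitis B viral DNA (HBV DNA) should be measured". The list that follows gives HBsAg positivity, without qualification, as item a) under seropositive or active infection. The Note to item b) admits patients who are negative for both HBsAg and viral DNA. Item c) adds as eligible "Patients who had HBV but have received an antiviral treatment and show no detectable viral DNA for 6 months" before the consent form is signed. Item d) admits the vaccination profile and states that HBsAg must be negative.

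**On-treatment rule, same section.** If HBV DNA becomes detectable, the patient is to receive antiviral treatment and be followed for reactivation. The patient may stay in the study only after assessment by a physician experienced in hepatitis B.

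**Tables.** Section 9.3.2.5 opens with "Clinical laboratory tests should be performed according to Table 10 and Table 11". Table 11 lists HBV DNA for anti-HBc-positive patients and marks it optional. Table 10 has a hepatitis B and C serology row. Its footnote 12 calls for local follow-up every 2 months in hepatitis B-positive patients and speaks of serology, not DNA. SAP Tables 2 and 4 repeat both wordings.

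**Pointers.** Synopsis exclusion 13 reads "Patients with known positive hepatitis B and/or C serology (as defined in the protocol"). The screening checklist in 9.2.2 has an entry "Viral testing: hepatitis B and C, CMV, HIV" linked to the virus serology text of 9.3.2.5.

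**The concern.** Protocol 4.5.3 lists hepatitis B reactivation among the anticipated possible risks of B-cell depletion, and safety is the primary objective. The protocol deliberately admits anti-HBc-positive, DNA-negative patients and relies on regular DNA testing to keep them safe. A site that orders tests from Tables 10 and 11, as 9.3.2.5 instructs, finds that test marked optional in one and unnamed in the other. If the site repeats serology alone, the reactivation safeguard has nothing to act on.

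The second issue is eligibility. Item c) says nothing about HBsAg, so a site relying on it could judge an HBsAg-positive patient with suppressed virus eligible, although 13a excludes that patient.

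**Working it through.** There is no planned figure to reproduce. The check sets the rules side by side.

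**1. HBV DNA test in anti-HBc-positive patients**

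| Source | At entry | On treatment |
|---|---|---|
| 7.2.2, 13a Note | Must be undetectable | DNA test every 2 months, compulsory |
| 9.3.2.5 text | Should be measured | Safeguard acts when DNA becomes detectable |
| Table 11 | Optional | Optional |
| Table 10, footnote 12 | DNA not named | 2-month interval given; DNA not named |

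Footnote 12 can be read with or without a comma after hepatitis B. On either reading DNA is absent. The omission is not forced by the format: footnote 14 of the same table names PCR for CMV monitoring. In Table 11 the parallel hepatitis C entry, RNA quantification if anti-HCV is positive, is not marked optional.

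**2. Eligibility by patient profile**

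| Profile | 13a and Note | 9.3.2.5 list | Result |
|---|---|---|---|
| HBsAg+, treated, DNA undetectable for 6 months | Excluded | a) seropositive or active; c) eligible | Conflict |
| HBsAg−, anti-HBc+, untreated, DNA undetectable | Allowed | b) Note: eligible | Agree |
| HBsAg−, anti-HBc+, treated, DNA undetectable for 3 months | Allowed | b) Note: eligible; c) 6-month condition not met | Unresolved |
| HBsAg−, anti-HBc−, HBsAb+ (vaccinated) | Allowed | d) eligible | Agree |

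The first row is the only direct contradiction. The third row shows that adding HBsAg-negative to item c) is not enough. Item c) would then cover only patients whom the item b) Note already admits without a waiting period, so its 6 months would be either redundant or a hidden extra condition.

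The 13a Note also omits HBsAg status. A patient positive for both markers with undetectable DNA fits its words. The better reading is that the Note lifts only the anti-HBc bar, but the text does not say so.

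**3. What the 13a monitoring amounts to**

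Assume a patient completes 24 cycles of 28 days, with the clock starting at C1D1: 24 × 28 = 672 days.

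- Taking 2 months as two cycles (56 days), tests fall at C3D1, C5D1, …, C23D1: (23 − 3)/2 + 1 = 11.
- Taking calendar months, with the 30.4375 days per month used in the SAP: 2 × 30.4375 = 60.875 days, and 672/60.875 = 11.04, again 11 tests.

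These 11 tests are already required by 13a. They show what footnote 12 should convey and are not a measure of risk.

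**The case against.** The strongest reply is that enrolment is already controlled. Section 7.2 makes 13a compulsory, Table 10 has the criteria checked at screening and again at C1D1, eligibility rests on central laboratory results, and exclusion 11b separately bars ongoing systemic viral infection. This largely stands. A reader might infer that the protocol permits enrolment of HBsAg-positive patients; it does not, because 13a governs and has no exception for them. A reader might also infer that the optional label lets anti-HBc-positive patients enter untested. It does not: without a DNA result the condition in the 13a Note is not met, and the patient remains excluded.

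Nor do the pointers show that sites are sent to item c) to decide eligibility. The synopsis wording most naturally leads to the same-numbered exclusion 13. In the 9.2.2 checklist the eligibility entry cites 7.2.1 and 7.2.2, and the link to virus serology belongs to the testing entry.

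Item c) also has a compatible reading, in which a patient who had HBV has cleared it. That is possible but not written. The item b) Note and item d) both state HBsAg negativity, and under the compatible reading item c) admits nobody whom the item b) Note does not.

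On monitoring, the reply is that 13a states the test, footnote 12 carries the interval, and the Laboratory Manual may supply the rest. The first two are true, but they do not remove the disagreement with the tables that sites are told to follow. The Laboratory Manual is not among the documents, so what sites would actually order is unknown.

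**Conclusion.** The concern holds as an internal inconsistency in patient-safety rules, minor to moderate in size.

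- **Main point.** Table 11 and Table 10 footnote 12 do not carry the HBV DNA requirement of 13a, and the reactivation safeguard depends on that test. This affects patients the protocol intends to admit.
- **Secondary point.** Item c), read literally, contradicts 13a for one group: HBsAg-positive, treated, with DNA undetectable for 6 months. The risk is limited to sites relying on item c).

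No sample size, endpoint or analysis is affected. The documents give no HBV prevalence, so the number of affected patients among the roughly 24 planned (about 12 per cohort) cannot be stated and may be zero. A reader might be tempted to gauge the size by counting the visits at which footnote 12 appears; that would count one wording defect many times over.

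The conclusion rests on taking 13a as the controlling rule, which 7.2 supports, and on the protocol text alone.

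**What to change.** Keep 13a as the controlling rule and make four wording changes in the protocol.

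1. **Table 11.** Replace the optional entry with: *HBV DNA: required if anti-HBc positive.*
2. **Table 10, footnote 12.** Reword to: *anti-HBc-positive patients: HBV DNA locally every 2 months.*
3. **Section 9.3.2.5, item c).** Align it with 13a by restricting it to HBsAg-negative patients, and settle the 6-month condition. Either state in item c), the item b) Note and the 13a Note that previously treated patients must also have had undetectable DNA for 6 months, or delete item c) as redundant with the item b) Note. The first option tightens entry for treated patients; the second leaves 13a as it stands. The choice is clinical.
4. **Section 7.2.2, 13a Note.** Add *HBsAg-negative* before the anti-HBc-positive patients it admits.

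SAP Tables 2 and 4 can be matched for consistency; that changes nothing at sites. The cost is wording only. No assay or visit is added, because 13a already requires the DNA test at the 2-month interval.
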